5.1.3 Removal of Subjects from the Study

Subjects will be informed that they are free to withdraw from the study at any time. Subjects should be questioned for the reason of premature withdrawal, although they are not obliged to disclose it. This needs to be fully documented in the Source Document and the electronic Case Report Form (eCRF).

When a subject withdraws or is removed from the study, the whole examination procedure planned on Day 6 must be performed as soon as possible after the time of withdrawal unless the subject has withdrawn their informed consent to do so. Subject will be informed that the whole examination procedure on Day 6 should be done for their safety but subjects will be free not to do it.

After the time of withdrawal, the subject will enter into the 7-day period of safety follow-up. Subjects withdrawn or removed from the study cannot re-enter the study.

Subjects must be withdrawn from the study for any of the following reasons:

- Withdrawal of informed consent.
- Any AE or condition (including clinically relevant changes in a laboratory parameter), at the discretion of the Investigator or designee.
- Positive pregnancy testing (any invasive procedures, including the drawing of blood MUST NOT be performed after diagnosis of pregnancy, see Section 8.5).
- The Sponsor or Investigator or designee terminates the study.
- Withdrawal is considered to be in the best interest of the subject or the other subjects.

Subjects may be discontinued from the study for any of the following reasons:

- Lost to follow-up.

Confidentiality statement: Data and information contained in this document are considered to constitute trade secrets and confidential commercial information, and the legal protections provided to such trade secrets and confidential information are hereby claimed under the applicable provisions of applicable law. No part of this document may be publicly disclosed without the written consent of Philip Morris Products S.A.

- Concomitant treatment with non-authorized medication as defined in the context of this study (in general, any concomitant medication should be discussed with the Contract Research Organization [CRO] Medical Monitor on an ongoing basis).
- If a subject uses any CC or nicotine/tobacco-containing product other than the product/regimen he/she is assigned to, it will be at the discretion of the Investigator or designee to decide whether or not to withdraw the subject from the study.
- Non-compliance to the study procedures.

Subjects withdrawn prematurely after randomization will not be replaced and will not be allowed to re-enter the study. All subject withdrawals have to be documented properly in the source documentation and the eCRF.

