 - THS 2.2 Arm: 80 subjects, ad libitum use of the product.
 - CC Arm: 40 subjects, ad libitum use of their preferred CC brand.
 - SA Arm: 40 subjects who will abstain from smoking.

Subjects will be informed of their randomized study arm by the study site staff on Day 1 prior to 06:30 AM.
- Exposure period (from Day 1, 06:30 AM until Day 5, 11:00 PM):

The exposure period will consist of 5 days of ad libitum use of the assigned product between 06:30 AM and 11:00 PM in THS 2.2 and CC arms. Use of any tobacco/nicotine-containing product other than the assigned product will not be allowed and may, at the discretion of the Investigator or designee, result in the subject withdrawal from the study.

Subjects in the SA arm will be asked to abstain from smoking any nicotine/tobacco-containing product and will not be provided with medication to support SA.

The end of the 24-hour urine collection period for Day 5 will end in the morning on Day 6 prior to Discharge.
- Day of Discharge (Day 6) (from Day 5, 11:01 PM to time of Discharge):

Procedures of Discharge, including but not limited to laboratory parameters, will be conducted to discharge the subject from the clinic after 9 days in a confined setting. Use of CC will be allowed on Day 6, but only after spirometry has been performed.
- Safety follow-up period (from Day 6, time of Discharge to Day 13):

Confidentiality statement: Data and information contained in this document are considered to constitute trade secrets and confidential commercial information, and the legal protections provided to such trade secrets and confidential information are hereby claimed under the applicable provisions of applicable law. No part of this document may be publicly disclosed without the written consent of Philip Morris Products S.A.

After time of Discharge, subject will enter a 7-day safety follow-up during which there will be recording of spontaneously reported new AEs/SAEs and the active follow-up of ongoing AEs/SAEs by the study site. In general, all AEs will be actively followed until resolved, stabilized (i.e., no worsening of the event), or a plausible explanation for the event has been found. The end of study (EOS) is defined as the time of Discharge on Day 6 plus 7-day follow-up period.

During the study, subjects in the CC and THS 2.2 arms who want to quit smoking will receive appropriate medical advice and will be referred to a smoking cessation counselor.

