6.4 Blinding

This is an open-label study; therefore, the subjects and Investigators or designees will be unblinded to the subject's arm. However, there will be a limited degree of blinding in the data review and data analysis process. In particular, PMI and CRO personnel will be blinded to the randomized arm as summarized in the following table:

| Blinded Study Personnel | End of Blinding Period |
|------------------------------------|--|
| PMI and CRO study statisticians | After the Statistical Analysis Plan (SAP) finalization or PMI blind database review ^(*) , whichever comes last. |
| PMI data manager | After the finalization of PMI blind database review. ^(*) |
| PMI safety and clinical scientists | After the finalization of PMI blind database review ^(*) . Can be actively un-blinded before that time point in case of the occurrence of any safety question, when appropriate. |

Abbreviations: CRO = Contract Research Organization; PMI = Philip Morris International.

(*) As part of the PMI quality control (QC) activity, data listings will be reviewed by PMI before database lock, with no access to the randomization arm information.

Any PMI and CRO personnel who are not listed in the above table will be unblinded by default.

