**Table 15. Time Schedule - Day 6**

| Time | Blood sample | Procedures | Additional information |
|---------------------------|--------------|--|--|
| Start of procedure | | Day of Discharge Day 6 | |
| | | AE/SAE recording; concomitant medication | All day until time of discharge |
| | √ | Nicotine, cotinine in plasma | 20 hours and 24 hours blood sampling after T0 of Day 5 for THS 2.2 and CC arms. Each sample has a time window of +/- 5 minutes For SA arm: 08:00 AM-10:00 AM |
| 06:29 AM+/- 30 min | | Analysis sample to be taken after final portion of urine has been added to Day 5 sampling bottle | BoExp, creatinine, and Ames mutagenicity in 24-hour urine Risk markers: 8-epi-PGF2 α and 11-DTX-B2 Bio-banking for BoExp/ risk markers in 24-hour urine (if additional consent is obtained) |
| | | Assessment of cough (VAS) | To be done prior to smoking but not later than 10:00 AM |
| | | MNWS questionnaire | To be done prior to smoking but not later than 10:00 AM |
| | √ | CYP2A6 activity in plasma | To be done prior to smoking |
| | | Spirometry without short-acting bronchodilator | To be done prior to smoking |
| | √ | Clinical laboratory parameters (hematology, clinical chemistry) | To be done after at least 8 hours of fasting |
| | √ | Bio-banking for BoExp/ risk markers in serum/plasma (if consent is obtained) | To be done after at least 8 hours of fasting |
| | √ | Bio-banking for transcriptomics (if consent is obtained) | To be done after at least 8 hours of fasting |
| Before discharge | | Urine safety analysis | |
| Before discharge | | Urine pregnancy test (all females) | |
| before 10:00 AM | | Breakfast | |

Confidentiality statement: Data and information contained in this document are considered to constitute trade secrets and confidential commercial information, and the legal protections provided to such trade secrets and confidential information are hereby claimed under the applicable provisions of applicable law. No part of this document may be publicly disclosed without the written consent of Philip Morris Products S.A.

| Time | Blood sample | Procedures | Additional information |
|------------------|--------------|--|--|
| Before discharge | | CO breath test | |
| Before discharge | | Physical examination, and weight and calculated BMI | |
| Before discharge | | Vital signs (blood pressure, pulse rate, respiratory rate) | At least 5 minutes in supine position prior to measurement |

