6.3.3 Compliance to Product Allocation

Compliance for all arms will be ensured by strict distribution of the products (product by product) and collection of used THS Tobacco Sticks and the CC butts after use will be documented in appropriate logs.

In addition, in subjects in the SA arm, the compliance will be chemically verified using exhaled CO breath. The cut-off point for the CO breath test value to distinguish subjects in the SA arm with CC use vs. no CC use will be 10 ppm (Bennowitz et al. 2002). No subjects from the SA arm will be withdrawn from the study if their exhaled CO breath test results are >10 ppm.

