10.1 Full Analysis Set

The FAS consists of all the randomized subjects who had at least one post-randomization product use experience, if randomized to THS 2.2 or CC, and have at least one valid BoExp measurement (THS 2.2, CC, SA arms).

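### A subject withdrawn before Day 5 for using a non-assigned product drops out of the Day 5 primary analysis, and this loss can favour THS 2.2

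*Protocol*

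**What the plan says.** **Withdrawal.** Protocol 4.1 says: "Use of any tobacco/nicotine-containing product other than the assigned product will not be allowed and may, at the discretion of the Investigator or designee", lead to withdrawal. Protocol 5.1.3 repeats that "it will be at the discretion of the Investigator or designee to decide whether or not to withdraw the subject from the study", and SAP 6.1 carries the same discretion. No criterion guides the choice. Protocol 6.4 says that "the subjects and Investigators or designees will be unblinded" to the arm. "Subjects withdrawn prematurely after randomization will not be replaced" (Protocol 5.1.3).

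**Samples after withdrawal.** For a withdrawn subject who still consents, "the whole examination procedure planned on Day 6 must be performed as soon as possible after the time of withdrawal". The Day 6 list (Protocol Table 15) has no COHb. Its only urine biomarker entry reads "Analysis sample to be taken after final portion of urine has been added to Day 5 sampling bottle". Protocol Table A1 schedules COHb no later than Day 5.

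**Analysis.** SAP 10.1 places a randomized subject in the FAS after one use of the product (THS 2.2 and CC arms) and one valid biomarker measurement; no Day 5 value is needed. SAP 12.6.1.1 models the last Day 5 COHb value and the Day 5 urine concentrations. SAP 12.1.5 says missing data are in general not imputed. Protocol 12.1.4 prescribes last observation carried forward (LOCF) for missing biomarkers of exposure. SAP section 9, which lists departures from the protocol's analysis, does not mention this one.

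**Robustness.** SAP Table 14 makes use of a non-assigned product a major deviation, considered for exclusion from PP (SAP 10.2). PP is a subset of the FAS and is assessed only if more than 10 subjects are excluded (SAP section 10). The confirmatory analysis is on the FAS only (SAP 12.6.1.2).

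**The concern.** The FAS is meant to carry the comparison as randomized, with PP as the adherent subset. If a THS 2.2 subject who smoked cigarettes is withdrawn before Day 5, that subject's Day 5 values are missing for a reason tied to both arm and outcome. They would probably have been among the highest in the arm. In the CC arm, losing a subject who switched to THS 2.2 removes a low value. Both losses move the THS 2.2 to CC ratio down, towards the 50% criterion. The decision is open-label and has no stated rule, so similar cases could be handled differently between arms.

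Whether the loss occurs depends on which missing-data rule applies. Under the SAP the subject leaves the model. Under the protocol an earlier value stands in. The two documents disagree, and the change is not declared.

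**Working it through.** **1. Route through the documents.** Take a THS 2.2 subject who has used THS 2.2, smokes a cigarette and is withdrawn on Day 3. FAS membership: yes (SAP 10.1). Day 5 COHb: none, since it is not a Day 6 procedure. Day 5 urine: none, since that collection was never started. Under SAP 12.1.5 the subject contributes to none of the four primary models. PP lacks the same values, so comparing FAS with PP cannot show the loss.

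**2. Plan's own figure.** Inputs: 80 versus 40 subjects, one-sided 2.5%, and the mean ratios (MR) and CVs of Protocol Tables 16 and 17. Log SD = sqrt(ln(1+CV²)); SE = SD × sqrt(1/80+1/40) = 0.1936 × SD; power = Φ(ln(0.5/MR)/SE − 1.96).
- COHb 0.40 (0.32): SD 0.312, SE 0.0605, 0.2231/0.0605 − 1.96 = 1.73, power 95.8%.
- COHb 0.44 (0.14): SD 0.139, SE 0.0270, 0.1278/0.0270 − 1.96 = 2.78, power 99.7%.

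Multiplying over the four biomarkers leaves 95.8% and 99.7%, against 96% and >99% in Table 18 (50% column). COHb decides the power. The ZRHX-EX-01 entries at 52% to 55% fit a CV near 0.12 better than the tabled 0.14; I use the tabled value.

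**3. Which endpoint is sensitive.** If a share f of the THS 2.2 arm sits at CC level, the ratio becomes MR^(1−f). It reaches 0.50 at f = 1 − ln(0.5)/ln(MR): 24% (MR 0.40) or 16% (MR 0.44) for COHb, and 42% to 74% for 3-HPMA, MHBMA and S-PMA. Only COHb is close.

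**4. Kept versus dropped.** Assume k of 80 THS 2.2 subjects have COHb at a fraction q of CC level. Both k and q are assumptions. The expected ratio if they are kept is MR^(1−k/80) × q^(k/80). For k = 4, MR 0.40 and q = 1 this is 0.40^0.95 = 0.419. Success means that the upper limit of the two-sided 95% interval is below 0.50 (two-sample t, 20,000 simulated trials, no covariates, SA arm left out).

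| COHb MR (CV) | q | Ratio kept / dropped (k = 4) | Success kept / dropped (k = 4) |
|---|---|---|---|
| 0.40 (0.32) | 1.0 | 0.419 / 0.400 | 75% / 95% |
| 0.40 (0.32) | 0.7 | 0.411 / 0.400 | 87% / 95% |
| 0.44 (0.14) | 1.0 | 0.458 / 0.440 | 63% / >99% |
| 0.44 (0.14) | 0.7 | 0.450 / 0.440 | 94% / >99% |

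With k = 2 and q = 0.7, success if kept is 92% and 98%. With k = 8 and q = 1.0 it is 40% and 4%. Dropping the subjects leaves it near 95% and above 99% throughout.

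**5. At the boundary.** Suppose the ratio over all 80 subjects is exactly 0.50, with 4 of them at CC level. The adherent subjects then have 0.50^(80/76) = 0.482. Dropping the 4 gives a success probability of 8.6% (CV 0.32) or 27% (CV 0.14), where the nominal limit is 2.5%.

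**The case against.** The best counter-argument is that this may seldom happen. Product is dispensed one unit at a time in confinement, butts are returned, smoking rooms are separate and the site holds the cigarettes. Withdrawal is an option, not a requirement. Protocol 4.2 puts the average half-life of the primary biomarkers at 24 hours or less, so an isolated early lapse would largely clear by Day 5, and full CC-level COHb is a worst case. All of this stands, and it limits the size of the problem. It does not supply a rule for the cases that occur.

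A second argument is that the protocol wants the effect of exclusive use, since Protocol 4.2 speaks of five days of it. But the SAP makes the FAS the confirmatory set and already handles use of other products through PP. An estimate in adherent subjects does not require losing Day 5 data.

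Three stronger readings are tempting, and the documents do not support them.
- A reader might infer that the FAS itself loses its non-adherers. It does not: SAP 10.1 keeps them, and only the Day 5 model loses them, under the no-imputation rule.
- A reader might infer different withdrawal rules by arm from SAP 6.3.3: "No subjects from the SA arm will be withdrawn from the study if their exhaled CO breath test results are >10 ppm". That sentence covers CO readings, which serve as a compliance test in SA only. Use detected in other ways in SA still falls under the discretion, and SA is outside the primary contrast.
- A reader might infer that a withdrawn subject can never have Day 5 data. Withdrawal during Day 5 may follow one or more of the four COHb samples, and withdrawal on Day 6 may follow the full urine collection.

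**Conclusion.** The concern holds as a gap in the plan that should be closed, not as evidence that bias will occur. An unblinded, discretionary decision can remove a subject's Day 5 values from the primary model for a reason related to the outcome. The direction can favour THS 2.2, and the planned PP analysis would not show it. Four such subjects would not on their own trigger that analysis.

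The size depends on an unknown number of subjects and on their COHb at Day 5. For 4 of 80, keeping rather than dropping them lowers the chance of meeting the COHb criterion by about 20 and 36 points in the worst case, and by about 8 and 6 points at 0.7 of CC level. The other three primary biomarkers are robust to this. If LOCF applied, the subject would stay in the model with an earlier value, so the conflict between Protocol 12.1.4 and SAP 12.1.5 decides whether the loss occurs.

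**What to change.** 1. In Protocol 4.1, 5.1.3 and the synopsis, and in SAP 6.1, state for all three arms that use of a non-assigned product is recorded as a deviation and is not by itself a reason to end data collection. Word the general non-compliance ground in 5.1.3 so that it does not reopen the same route.
2. From subjects who still consent, take the Day 5 COHb samples and the Day 5 24-hour urine as already scheduled. Analyse them as randomized in the FAS and exclude them only from PP, under Table 14. Withdrawal for consent, adverse event, pregnancy or best interest is unchanged.
3. Choose between LOCF and no imputation for missing primary biomarkers, align Protocol 12.1.4 with SAP 12.1.5, and list the change in SAP section 9.
4. Add a sensitivity analysis for Day 5 values missing after such withdrawal, for example with the subject's own baseline or CC-arm levels substituted. Report the number of such withdrawals by arm.

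The cost is a few sentences in two documents and one extra analysis, with no new procedures. Steps 1 and 2 help only while subjects are still in the study. Steps 3 and 4 can be made until database lock (SAP section 3). The downside is that the reported reduction may be slightly less favourable.

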5.1.4 Violation of Selection Criteria

Subjects who are eligible at Screening, but who do not meet the entry criteria at Admission Day (Day -2), will be considered a screening failure until enrolment and will be replaced by other subjects.

Subjects who violate the entry criteria prior to enrolment, but who were considered eligible, will be immediately withdrawn from the study when the violation is detected. If subjects are not yet randomized, they can be replaced.

6 INVESTIGATIONAL PRODUCTS

6.1 Description of Investigational Products

6.1.1 Test Product

THS 2.2 comprises the following components: Tobacco Stick, Holder, Charger, a Cleaning Tool, a mains power supply, and a USB cable:

Charger: The function of the Charger (Model 4) is to recharge the Holder after use. It contains a battery with sufficient capacity to recharge the Holder approximately 20 times. It is a convenient size to carry around, and can itself be recharged from a mains power source.

THS Tobacco Stick Holder (Holder): The function of the Holder (Model 4.2) is to heat the Tobacco Stick, delivering an aerosol to the user. The electrical heating is powered from an internal battery which delivers power for about 6 minutes (allowing complete use of a single Tobacco Stick)

THS Tobacco Stick (Tobacco Stick): The Tobacco Stick (product code C3) contains tobacco which, when heated, generates an aerosol. It is custom-designed to be used with the Holder.

The overall objective of the product design is to provide an acceptable experience in which the HPHC levels in the aerosol are substantially reduced in comparison with CC.

The THS 2.2 will be provided by the Sponsor.

Per cigarette/Tobacco Stick tar, nicotine, and carbon monoxide yields are normally determined by standardized test methods. The most widely used test method is ISO 4387. PMI has developed a modified version of this method, which improves the determination of tar in products with high water content, which is typical for heated tobacco products (PMI, 2012a, PMI, 2012b, PMI, 2013b). Another method is the more intensive smoking method developed by Health Canada (Health Canada, 1999).

Table 1 below lists the commonly reported measures (PMI, 2013a).

**Table 1 Measured aerosol fractions for the THS Tobacco Sticks**

| Constituent (mg/THS Tobacco Stick) | ISO ¹ | Health Canada Intense regime ² |
|------------------------------------|------------------|---|
| Tar/NFDPM | 4 | 10.3 |
| Nicotine | 0.5 | 1.32 |
| Carbon monoxide | 1 | 0.6 |

¹ International Organization for Standardization ISO machine-smoking regimen. The analytical method has been modified to avoid inaccuracies as a result of condensation from high water-content aerosols.

² Health Canada Intense machine-smoking regimen (55 mL puff volume, 2-second puff duration, 30-second inter-puff interval) (Health Canada, 1999)

6.1.2 Reference Product / Baseline Period Products

During the run-in period (Admission to clinic until 06:29 AM of Day -1) and the baseline period (from 06:30 AM of Day -1 until 06:29 AM of Day 1), all subjects will continue smoking their preferred commercially available single brand of non-menthol CC. Subjects are not allowed to roll their own CC.

The reference product to the THS 2.2 during the randomized exposure period is the subject's own preferred commercially available single brand of non-menthol CC.

All eligible subjects will be asked to purchase their own preferred single brand CC prior to Admission and provide his/her anticipated amount of CC for a total of 9 days plus 4 extra packs on Day -2 (Admission Day) to the site staff. The CCs will not be provided by the Sponsor.

6.1.3 Packaging and Labeling

At Admission, all study subjects will provide the anticipated amount of CC in sealed packs to the study site staff. The CC packs provided by the subjects should not be opened and the cellophane wrapper should be intact.

Each pack of CC provided by the subject will be labeled to identify which subject the CCs belong to (labels should be affixed to the cellophane wrapper of the lower part of the pack). Each pack of CCs will be labeled to identify necessary information to match the subject with its suppliers.

For the Tobacco Sticks, the packs will be printed with the necessary information including but not limited to health warning, tar/nicotine/CO ISO levels, product code.

6.2 Use of Investigational Product(s)

Subjects will never be requested or forced to smoke and will be free to stop smoking at any time during the study. The study is designed as an *ad libitum* use study. During the Confidentiality statement: Data and information contained in this document are considered to constitute trade secrets and confidential commercial information, and the legal protections provided to such trade secrets and confidential information are hereby claimed under the applicable provisions of applicable law. No part of this document may be publicly disclosed without the written consent of Philip Morris Products S.A.

confinement period, smoking will generally be allowed between 06:30 AM to 11:00 PM. During the screening period, subjects will be allowed to smoke according to their smoking habits except during the procedures of the Screening Visit at the discretion of the site.

